#### **6.4 Recruitment and informed consent**

Subjects will be recruited into the study according to the following steps:

1. Patients with type 1 diabetes will be identified by their local diabetes teams (hospital doctors or diabetes nurses), from clinic records, during clinic visits or inpatient admissions.
2. Some patients may self-refer and contact the trial team directly, from seeing internet information, news articles or posters regarding participating in diabetes research, or be identified by the ADDRESS-2 registry of recently diagnosed patients with type 1 diabetes. Patients who self-refer will have their details passed to the local coordinator of the study or research nurse/doctor and will be contacted initially by phone, email or in person by the local centre research team who will outline and explain the aim of the study and provide copies of the Participant Information Sheet (PIS).
3. For subjects identified by health records or clinical contacts, the study will be discussed with the identified patients by a member of their clinical care team and, with the subject's agreement, details will be passed to the local coordinator of the study.
4. Subjects who have consented to be on the ADDRESS2 registry and consented to be contacted regarding research that they may be eligible to take part in, will be contacted initially by the lead centre.
5. Subjects will then be contacted by phone, email or in person by the local centre research team who will outline and explain the aim of the study and provide copies of the Participant Information Sheet (PIS).
6. Subjects will have a minimum of 24 hours to consider this information and usually at least 5-7 days. Subjects will be invited to call the local research nurse or Local Principal Investigator for any queries about the PIS and to indicate if they wish to take part.
7. An appointment will then be made for interested subjects, at which the Local Principal Investigator or their appointed deputy can check the subject's understanding of the study and obtain written consent. Subjects may then take part in assessments required for the first screening visit (visit -2).

8. If the subject has the HLA *DRB1\*0401* genotype then the local research team will arrange an appointment with him/her for the second screening visit (visit -1) which will include a post meal UCPCR or random serum c-peptide, blood samples and urine pregnancy test (if female).
9. If appropriate, screening visits -2 & -1 can be combined.
10. Subjects who fulfil all inclusion criteria without exclusion criteria will be informed of their screening results, and arrangements made for enrolment and the first study visit.
11. A schedule of study visits and procedures carried out at each study visit are shown in table 1.
12. Where the start of dosing is delayed more than three months beyond screening visit - 1, all the tests and physical assessment required at screening (excluding genotyping) should be repeated to confirm continues eligibility.

### 6.5 General assessments

General assessments for this protocol are:

- Inclusion/exclusion criteria
- Medical history
- Physical examination & ECG recording
- Concomitant medications
- Adverse event recording
- Record of insulin usage
- Assessment of glycaemic control
- Quality of life questionnaires
- Photographs at injection sites at each visit

### 6.6 Follow up assessments

The primary outcome measure for the trial is the safety (adverse event) profile of this investigational agent.

The key components of the follow-up visits are:

1. Diabetes assessments;
2. Adverse events;
3. Any changes in medications;
4. Review of clinical safety blood tests.

### 6.7 General laboratory tests

A study specific laboratory manual will be provided and the following general laboratory assessments will be performed during the study:

- Full blood count; urea, electrolytes and creatinine; liver function tests (prothrombin time, total bilirubin, total protein, albumin, AST (SGOT), SGPT (ALT), alkaline phosphatase; thyroid stimulating hormone; immunoglobulins (G, A, M); calcium; magnesium, phosphate, lipid profile (total cholesterol, LDL, HDL, triglyceride). These will be tested in the local laboratories of the study sites.
- Urine pregnancy test (females only, at all trial visits)
- Urinalysis for pH, blood and protein by dipstick urinalysis and laboratory analysis for albumin/creatinine ratio, urine beta-2-microglobulin and cystatin-C.
- Autoantibodies against insulin, GAD-65, IA-2 and ZnT8 (performed in the Diabetes Research Unit Cymru Laboratories, Swansea University)
- Anti-drug (GNP-peptide C19-A3) antibodies

### **6.8 Study Drug Administration**

Study subjects will attend a clinical research facility or hospital ward (Linköping) for receiving the IMP. Staff will be experienced in CTIMPs and facilities for managing a severe reaction will be to hand (see section 10.2). The drug will be prepared and injected intradermally in the upper arm of the patient in a 50ul volume, according to the schedule (see figure 2).

All subjects will be observed 6 hours after their first dosing/injection, however the first subject will be dosed at least 24 hours before subsequent subjects as per sentinel dosing strategy (see risk mitigation strategy section 7). If no SAEs are observed after this first dose, all subjects will be observed for a minimum of one hour after each injection and up to 2 hours if there are any signs of hypersensitivity. All local and systemic reactions will be documented.

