## **4 TRIAL OBJECTIVES AND DESIGN**

### **4.1 Trial Objectives**

The primary objective of the study is to examine the risk of C19-A3 GNP administration in terms of general safety and induction of hypersensitivity.

Secondary objectives are:

- To study the feasibility of delivering C19-A3 GNP via microneedles to humans.
- To study the size and nature of immune responses to C19-A3 GNP generated in blood and the draining (axillary) lymph node.

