**All serious adverse events will be shared within 24 hours with the other recruiting site.**

**Sentinel dosing.** The first patient dosed with GNP-peptide will be observed for 6 hours post dose. Temperature, blood pressure and heart rate will be recorded at the following intervals post injection: 15 mins, 30 mins, 45 mins, 1 hour, 1 hour 30mins, 2 hours, 2 hours 30 mins, 3 hours, 4 hours, 5 hours and 6 hours. The injection site will be observed at the following intervals post injection: 5mins, 10 mins, 15 mins, 30 mins, 45 mins and 1 hour. A follow-up phone call will be made to the subject 24 hours after the first dose. No additional patients will be able to be recruited until this 24 hour period is completed (“lock-out period”).

If no serious adverse events are observed, subsequent subjects will also be observed for 6 hours after their first injection. If no serious adverse events are observed, then subjects will be observed for a minimum of 1 hour post dose, or 2 hours if there are any symptoms of signs of hypersensitivity. This time period has been chosen as the only anticipated severe reactions is one of hypersensitivity which, if systemic, would be apparent within 60 mins of intradermal dosing. See section 10.2 for further discussion of hypersensitivity.

Each subject will be contacted by telephone 24 hours after each dose.

The trial manager will communicate with clinical staff by email and telephone to keep both sites up to date with screening and recruitment activity. Weekly teleconferences between sites will take place during the screening and recruitment phase and the trial manager will inform clinical staff at both sites when the first patient is going to be dosed and report to them afterwards regarding whether any AE's were experienced. This will negate the possibility of two subjects starting treatment on the same day. Close communication between sites will be maintained throughout the trial and details of any adverse reactions will be communicated to the other trial treatment site by email, in addition to the standard pharmacovigilance procedures.

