## 10.2 Hypersensitivity

Induction of hypersensitivity to C19-A3 GNP will be assessed by a period of observation of subjects and during the immediate period after peptide injection. Local hypersensitivity may manifest as an increasing wheal and flare reaction at the site of peptide injection. The first patient dosed with GNP-peptide will be observed for 6 hours post dose – see section 7.3. Any adverse reactions will be communicated to the other trial treatment site by email, in addition to the standard pharmacovigilance procedures. Subsequent subjects will also be observed for 6 hours. If no serious adverse events are observed post first dose, subsequent visits will have an observation period of a minimum of 1 hour post dose, or 2 hours if there are any symptoms of signs of hypersensitivity. This time period has been chosen as the only anticipated severe reactions is one of hypersensitivity which, if systemic, would be apparent within 60 mins of intradermal dosing.

Observation will be by inspection of the injection site at 5 minute intervals for the first 15 minutes and then 15 minute intervals for a further 45 minutes. If any reaction is present and not resolving over this period, observation will be extended to 15 minute intervals until the reaction is reducing and < 1cm in diameter. Maximum size of any redness or swelling at the injection site will be recorded at each visit at which study drug is given (visits 1-3). Systemic hypersensitivity may manifest as shortness of breath; skin rash; tissue swelling; collapse. Subjects will be inspected for such signs at 5-minute intervals for the first 15 minutes and then at 15 minute intervals for a further 45 minutes. Pulse and blood pressure will be recorded at 15 minute intervals over this time. Any adverse events during this observation period will be recorded. To minimise any risk that might result from hypersensitivity:

- IMP administration should ONLY performed in a clinical research environment appropriate for phase 1 studies in which resuscitation facilities are immediately available.
- Facilities for treatment of a major hypersensitivity reaction, adrenaline, oxygen, intravenous infusion, head-down position, blood pressure and pulse monitoring should be available in the immediate environment of the subject, with access to hydrocortisone and antihistamines.
- Subjects should not be treated by a lone-worker unless he/she has immediate access to clinically trained support.

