5.1. Analysis of outcomes

5.1.1. Primary outcome

Assessment of the safety of C19-A3 GNP administration in terms of adverse events at the dose used is the primary outcome. This includes general safety concerns, induction of hypersensitivity and exacerbation of β -cell specific autoimmunity with accelerated β -cell loss. All enrolled patients will be included in the following analysis.

General Safety

To address general safety concerns at screening and 0, 4, 8 and 14 weeks a physical examination will be conducted. A review of AEs will be performed at all visits according to seriousness, causality and expectedness. Types of AEs, body systems involved and outcomes of the AE will be categorised and analysed by incidence per person dose used. All AEs will be collated

Hypersensitivity

Patients will be observed for local and systemic reactions post injection. Number of local reactions will be analysed by incidence per person dose used, size of the erythema note and time taken for erythema note size to be reduced to < 1 cm will be analysed by mean and standard deviation. Systemic reactions will be analysed by incidence per person dose used. Therapies used and outcome will be counted and reported.

Exacerbation of β -cell specific autoimmunity with accelerated β -cell loss

Differences between week 0 and 14 will be calculated for each patient and summarised by mean and standard deviations for the following parameters:

- Measurement of islet cell autoantibodies (against insulin, GAD-65, IA-2 and ZnT8)
- Measurement of pro-inflammatory β -cell specific T cell responses (analytes to be defined)

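### SAP 5.1.1 reports local and systemic reactions per person-dose with no split by dose number, so it cannot show whether reactions change after repeated dosing

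*Protocol*

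**What the plan says.** Protocol 4.1 and SAP 1.2 set the primary objective as the risk of administration "in terms of general safety and induction of hypersensitivity". SAP 5.1.1 gives the summary: "Systemic reactions will be analysed by incidence per person dose used". The number of local reactions is handled in the same way. I read this as events divided by doses given. Neither that section nor the dummy tables in SAP Appendix 1 split reactions by dose number.

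Direct observation is described in three places in the protocol:

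- Section 6.8: "All subjects will be observed 6 hours after their first dosing/injection". The rule that then applies, provided dose 1 brought no serious adverse event, reads "all subjects will be observed for a minimum of one hour after each injection and up to 2 hours if there are any signs of"; the signs meant are those of hypersensitivity.
- Section 10.2: "subsequent visits will have an observation period of a minimum of 1 hour post dose", or 2 hours with signs or symptoms. The reason given is that a severe hypersensitivity reaction, "if systemic, would be apparent within 60 mins of intradermal dosing".
- Section 10.2 also sets a structured check for systemic signs: "Subjects will be inspected for such signs at 5-minute intervals for the first 15 minutes", then every 15 minutes for a further 45 minutes, with pulse and blood pressure. This schedule is not varied by dose.

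Detection continues after the subject leaves. Protocol section 7 says "Each subject will be contacted by telephone 24 hours after each dose". Protocol Table 1 marks adverse-event assessment at visits 1b and 1C after dose 1, at 3b and 3C after dose 3, and at all later visits.

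**The concern.** Induction is a statement about change with exposure. A subject who becomes sensitised would be expected to react at dose 2 or 3 rather than at dose 1, so the informative comparison is between dose numbers. One incidence over all person-doses averages that comparison away, however long subjects are watched. A reader of the final report could see a moderate overall rate and be unable to tell whether it was constant or had climbed from nothing.

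The unequal observation time is a second reason to separate the doses. A count at dose 1 can include directly observed reactions up to 6 hours. A count at a later dose may rest on 1 hour of direct observation plus a telephone call and later visits. Adding the two without a label mixes different ways of finding a reaction.

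**Working it through.** The plan gives no rate, power or formula for this endpoint, and SAP section 4 says the sample is not powered, so there is no planned figure to reproduce.

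**Inputs.** 8 subjects who receive all 3 doses (Protocol 5.4, SAP 4.1); 6 hours of observation at dose 1 and a minimum of 1 hour at doses 2 and 3 (Protocol 6.8, 10.2).

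**Step 1: what pooling hides.** Person-doses = 8 × 3 = 24.

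- Rising pattern: 0/8, 2/8, 4/8 gives (0 + 2 + 4)/24 = 6/24 = 25%.
- Flat pattern: 2/8, 2/8, 2/8 gives (2 + 2 + 2)/24 = 6/24 = 25%.

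The SAP summary is identical for both; a by-dose table separates them. The result does not depend on observation time.

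**Step 2: denominators.** Protocol section 7 and SAP 2.2.2 stop dosing in subjects with certain reactions, so reactors may leave the later denominators. If 2 of 8 stopped after dose 1 and were not replaced, the numbers dosed would be 8, 6 and 6. A pooled denominator of 20 does not show this.

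**Step 3: scheduled direct observation.** Dose 1: 8 × 6 = 48 hours. Doses 2 and 3: 16 × 1 = 16 hours at the minimum. Dose 1 is one third of doses and has 48/64 = 75% of the scheduled time, or 48/(48 + 32) = 60% if every later dose ran to 2 hours.

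**Step 4: when the shorter window would matter.** Let p be the true systemic reaction rate at later doses, f the share of those reactions starting after hour 1, and q the share of these late reactions recovered by the call or adverse-event review. Assume capture at dose 1 is complete. Then

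recorded rate = p × [1 − f(1 − q)].

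The documents give neither f nor q; both are assumptions. Taking p = 30% for illustration:

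| f | q | Recorded rate |
|---|---|---|
| 0 (protocol's premise) | any | 30% |
| 0.3 | 0 | 0.30 × 0.70 = 21% |
| 0.3 | 0.5 | 0.30 × 0.85 = 25.5% |
| 0.3 | 0.9 | 0.30 × 0.97 = 29.1% |

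To make a true r-fold rise look flat, f(1 − q) must reach 1 − 1/r: 33% for r = 1.5, 50% for r = 2 and 67% for r = 3.

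**Step 5: precision of the by-dose table.** With no events, the one-sided 95% upper limit is 1 − 0.05^(1/n): 31.2% for n = 8, 17.1% for n = 16 and 11.7% for n = 24. The limits for 16 and 24 treat doses in one subject as independent. On the same assumption, 0/8 against 4/8 gives Fisher p = 0.077.

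**The case against.** The strongest reply is that little is hidden. The SAP is descriptive, all adverse events are collated, and therapies and outcomes are counted. The data files carry the treatment number, so any event can be traced to its dose. Anti-drug antibodies (Protocol 6.7) and optional patch testing (Protocol 6.15) also bear on induced hypersensitivity. This stands as far as it goes: the information exists. But the summary specified for the primary outcome does not show it, and leaving the split to be chosen after the data are seen is weaker than specifying it now.

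A reader might go further and infer that 6 hours against 1 hour hides sensitisation at later doses and biases the safety conclusion towards reassurance. The documents do not support that:

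- The structured first-hour inspection covers systemic signs as well as the injection site, and it is not varied by dose.
- One hour is a minimum, extended when signs appear. That extension does not help with a reaction that starts after the subject has left.
- Late reactions can still be recorded through the 24-hour call after each dose and adverse-event review at visits. Dose 3 has the same next-day and day 3 to 5 visits as dose 1; dose 2 has neither and relies on the call until the next scheduled visit.
- On the protocol's premise of onset within 60 minutes, nothing is lost. The premise is asserted without onset data, so it can be questioned, but nothing in the documents contradicts it.

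**Conclusion.** The concern holds for the summary measure. SAP 5.1.1 cannot distinguish a rise across doses from a constant rate, although that distinction is part of the primary objective; the 25% example shows this without any assumption about onset or detection.

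Bias from the shorter observation is not established. Its size runs from nil, under the protocol's premise, to an amount set by f(1 − q), which the documents do not allow anyone to estimate. It is a reason to label how reactions were found, not a finding that later reactions will be missed.

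The improvement is modest. With 8 subjects per dose, a by-dose table describes the pattern and cannot test it. This concerns analysis and reporting only and takes no position on how long subjects should be observed.

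**What to change.** In SAP 5.1.1:

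1. Add a table of local and systemic reactions by dose number (1, 2, 3), with the number of subjects dosed at each dose as denominator. Keep the pooled per-person-dose figure beside it and state that the table is descriptive.
2. Base the between-dose comparison of systemic reactions on the 60-minute structured inspection in Protocol 10.2.
3. List systemic reactions found after that inspection separately by dose, with the source (direct observation, 24-hour call, later visit) where the CRF records it.

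Item 1 costs only SAP wording and one table. The SAP's clinical-observation file (Table 5 of the data-file specification) already holds visit and treatment number, and the adverse-event file (Table 8) holds treatment number. Items 2 and 3 are not shown to be free: Table 8 lists start and end dates but no onset time or detection source, so they may need CRF review or an added field. No visit or procedure changes.

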### **6.9 Metabolic outcome assessments**

Metabolic assessments will consist of:

- Glucose records and reports of hypoglycaemia (clinical care measurement)
- Insulin dose (clinical care measurement)
- HbA1c level (laboratory test)
- Urine or random serum post-meal c-peptide/creatinine ratio (laboratory test)
- Mixed meal tolerance test (MMTT) (laboratory test)

Laboratory measurements for these will be performed in the laboratories of the Diabetes Research Unit Cymru laboratory, Swansea University.

### **6.10 Mechanistic immunological studies**

Mechanistic assessments will consist of:

- Ultra-sound guided Axillary LN aspiration and ELISPOT data before and 3-5days after administration of the first dose and the final dose of IMP (total of 4 aspirations for each patient)

- T cell assays to include enzyme-linked immunospot (ELISPOT) to measure T cell responses to PPI C19-A3 and other islet cell autoantigenic peptides using LN cells and fresh whole heparinised blood sent by courier to the assay laboratory
- Storage of peripheral blood mononuclear cells (PBMCs) for subsequent analysis of T cell responses (measurement of Tregs and antigen-specific T cells by tetramer and Diab-Q-kit)
- Storage of DNA for subsequent analysis of gene-phenotype interactions
- Storage of serum for islet autoantibody assessments and cell free DNA measurements
- Additional mechanistic assays by the T1D UK Consortium Mechanistic Core

### **6.11 General guidance on glycaemic control during the study**

Glycaemic control will be maintained according to clinical guidelines and conducted in collaboration with the patient's diabetes health care team.

- HbA1c will be measured every 1-3 months with a target value set by agreement with the patient and their clinical care team. Where this target is not met, advice will be given as clinically required.
- Glycaemic control will be reviewed at every study visit.
- Where insulin requirements fall to less than a total of 8 IU per day, continuation of insulin therapy should be discussed with the Chief Investigator: continuation of a low dose of insulin where possible is considered preferable.

### **6.12 Ultrasound guided Fine Needle Aspiration of axillary lymph node**

Ultrasound guided Fine Needle Aspiration of axillary lymph node (US-guided FNA) will be performed by an experienced consultant radiologist, before and after Visits 1 and 3.

The procedure is as follows: Under aseptic technique and ultrasound guidance and following local anaesthetic, a 21G needle is inserted into an axillary lymph node and few drops of fluid aspirated and sent for immunological studies (as in section 6.10).

### **6.13 Optional Skin biopsy and blister sampling.**

To determine how long the gold nanoparticles stay in the skin and the immunological effects, subjects will be invited to undergo an optional skin biopsy and an optional suction blister. In order not to disturb the systemic effects of nanoparticle administration, skin sampling will not be performed until after visit 3 (post final dose). For the optional skin biopsy, a 4mm skin biopsy using standard dermatological techniques will be taken at the site of the first injection (ie 2 months after the final dose) to determine residual gold distribution. For the optional suction blister, a standard suction blister sample (82,83) will be taken from the site of the second injection (ie 1 month after the final dose) to study any infiltrating lymphocytes (83).

Skin biopsies will be taken by a 4mm standard punch technique. The material obtained will snap frozen for immunohistochemistry and gold staining and part stored for RNA extraction and PCR/RNA seq analysis.

Skin suction blisters will be performed by gradually applying negative pressure (up to 50 kPa) from a suction pump machine VP25 (Eschmann, Lancing, UK) through a suction blister cup with a 15-mm hole in the base for 2–6 hr until a unilocular blister had formed within the cup. The blister fluid is then aspirated after blister formation and spun to obtain any infiltrating lymphocytes. These will be analysed for reactivity to the administered peptide by ELISPOT and for surface molecule expression by cytopins and fluorescence microscopy if sufficient sample is obtained.

